# 13 DATA HANDLING AND ADMINISTRATIVE REQUIREMENTS

# 13.1 Subject Confidentiality

The investigator must ensure that the subject's identity is kept confidential throughout the course of the study. In particular, the investigator must keep an enrollment log with confidential identifying information that corresponds to the subject numbers and initials of each study participant. The study sponsor may collect a copy of the enrollment log without any directly identifying subject information.

The study sponsor may share patient-level data collected in this trial with qualified researchers to help facilitate product development or enhancements in research that is not directly related to the study objectives. The informed consent explains this to the study subject.

# 13.2 Completion of Source Documents and Case Report Forms

The nature and location of all source documents will be identified to ensure that original data required to complete the CRFs exist and are accessible for verification by the site monitor, and all discrepancies shall be appropriately documented via the query resolution process. Site monitors are appointed by the study sponsor and are independent of study site staff.

If electronic records are maintained, the method of verification must be determined in advance of starting the study.

At a minimum, source documents include the following information for each subject:

- Subject identification (name, sex, race/ethnicity)
- Documentation of subject eligibility
- Date of informed consent
- Dates of visits
- Documentation that protocol-specific procedures were performed
- Results of study parameters, as required by the protocol
- IP accountability records
- Documentation of AEs and other safety parameters (if applicable)
- Records regarding medical histories and the use of concomitant therapies prior to and during the study
- Date of study completion and reason for early discontinuation, if applicable

It is required that the author of an entry in the source documents be identifiable. Direct access to source documentation (medical records) must be allowed for the purpose of verifying that the data recorded on the CRF are consistent with the original source data.

Only designated individuals at the site will complete the CRFs. The CRFs must be completed at regular intervals following the clinical study visit schedule. It is expected that all data reported have corresponding entries in the source documents. The principal investigator is responsible for reviewing and certifying that the CRFs are accurate and complete. The only subject identifiers recorded on the CRFs will be subject number, and subject demographic information.

#### 13.3 Data Review and Clarifications

A review of CRF data to the subject's source data will be completed by the site monitor to ensure completeness and accuracy. After the CRFs have been completed, additional data clarifications and/or additions may be needed as a result of the data cleaning process. Data clarifications are documented and are part of each subject's CRF.

# 13.4 Sponsor and Monitoring Responsibilities

The study sponsor will select principal investigators that are qualified by education, training, and experience to assume responsibility for the proper conduct of this clinical trial. For this study, the principal investigator and implanting sub-investigators must be healthcare professionals appropriately trained/licensed/certified to perform surgery/treat subjects with the condition under study.

The study sponsor is financially funding this clinical trial and will compensate the investigator and/or the institution(s) at which the study is conducted in accordance with a signed clinical trial agreement.

The study sponsor will designate a monitor to conduct the appropriate site visits at the appropriate intervals according to the study monitoring plan. The clinical investigation will be monitored to ensure that the rights and wellbeing of the subjects are protected, the reported data are accurate, complete, and verifiable from the source documents, and the study is conducted in compliance with the current approved protocol (and amendments[s], if applicable), with current GCP, and with applicable regulatory requirements.

The site may not screen subjects or perform the informed consent process on any subject until it receives a notification from an appropriate study sponsor representative that the site may commence conducting study activities. Monitoring will be conducted periodically while the clinical study is ongoing. Monitoring methods may include site visits, telephone, written, and fax correspondence. Close-out visits will take place after the last visit of the last subject at the site.

A coordinating investigator may be identified by the study sponsor to review and endorse the final study report. In cases where a coordinating investigator is engaged, the study sponsor will select the coordinating investigator based upon their experience, qualifications, active study participation, and their willingness and availability to take on this role.

# 13.5 Regulatory Documentation and Records Retention

The investigator is required to maintain up-to-date, complete regulatory documentation as indicated by the study sponsor and the investigator's files will be reviewed as part of the ongoing study monitoring. Financial information is to be kept separately.

Additionally, the investigator must keep study records and source documents consistent with the terms of the clinical study agreement with the study sponsor. If the investigator retires, relocates, or for any other reason withdraws from responsibility of keeping the study records, then the study sponsor must be notified, and suitable arrangements made for retention of study records and source documents needed to comply with national and international regulations.

# 13.6 Quality Assurance and Quality Control

The study sponsor will secure agreement from all involved parties to ensure direct access to all study related sites, source data and documents, and reports for the purpose of monitoring and auditing by the study sponsor, and inspection by domestic and foreign regulatory authorities. Quality control will be applied to each stage of data handling to ensure that all data are reliable and have been processed correctly. Agreements made by the study sponsor with the investigator/institution and any other parties involved in the clinical study will be provided in writing as part of the protocol or as a separate agreement.

#### 14 ETHICS

Investigations are conducted in compliance with GCP; international and national regulations, laws and guidelines; ISO 14155; the conditions of approval imposed by reviewing IRBs/IECs or regulatory authorities; and in accordance with the ethical medical research principles outlined in the Declaration of Helsinki.

- The SOPs of the study sponsor and contract research organizations participating in the conduct of the clinical study and all other applicable regulations shall apply.
- Notifications and timelines for reporting protocol deviations should be based upon applicable ethics committee requirements.

The investigator must ensure that all personnel involved in the conduct of the study are qualified to perform their assigned responsibilities through relevant education, training, and experience. The investigator and all clinical study staff must conduct the clinical study in compliance with the protocol. The investigator is not allowed to deviate from the protocol except to protect the rights, safety, and wellbeing of human subjects under emergency

circumstances. Emergency deviations may proceed without prior approval of the sponsor and the IRB/EC, but shall be documented and reported to the sponsor and the IRB/EC as soon as possible. Deviations from this protocol, regulatory requirements, and/or GCP must be recorded and reported to the sponsor prior to database lock. If needed, corrective and preventive action should be identified, implemented, and documented within the study records. Failure to implement identified corrective and preventative actions may result in site closure by the sponsor. Use of waivers to deviate from the clinical protocol is prohibited.

Before clinical study initiation, this protocol, the informed consent form, any other written information given to subjects, and any advertisements planned for subject recruitment must be approved by an IRB/IEC. The investigator must provide documentation of the IRB/IEC approval to the study sponsor. The approval must be dated and must identify the applicable protocol, amendments (if any), informed consent form, assent form (if any), all applicable recruiting materials, written information for subject, and subject compensation programs. The IRB/IEC must be provided with a copy of the IFUs, any periodic safety updates, and all other information as required by local regulation and/or the IRB/IEC. Any additional requirements imposed by the EC or regulatory authority shall be followed. At the end of the study, the investigator must notify the IRB/IEC about the study's completion. The IRB/IEC also must be notified if the study is terminated prematurely. Finally, the investigator must report to the IRB/IEC on the progress of the study at intervals stipulated by the IRB/IEC.

Voluntary informed consent must be obtained in writing from every subject. The obtaining of consent shall be documented before any procedure specific to the clinical investigation is applied to the subject.

The investigator must have a defined process for obtaining the required consent. Specifically, the investigator, or their delegate, must explain the clinical study to each potential subject and the subject must indicate voluntary consent by signing and dating the approved informed consent form. The subject must be provided an opportunity to ask questions of the investigator, and if required by local regulation, other qualified personnel. The investigator must provide the subject with a copy of the consent form written in a language the subject understands. The consent document must meet all applicable local laws and provide subjects with information regarding the purpose, procedures, requirements, and restrictions of the study, along with any known risks and potential benefits associated with the IP and the study, the available compensation, and the established provisions for maintaining confidentiality of personal, protected health information. Subjects will be told about the voluntary nature of participation in the study and must be provided with contact information for the appropriate individuals should questions or concerns arise during the study. The subject also must be told

that their records may be accessed by appropriate authorities and sponsor-designated personnel. The investigator must keep the original, signed copy of the consent (file in subject's medical records) and must provide a duplicate copy to each subject according to local regulations.

The investigator should document subject withdrawal of consent. The investigator is the designated contact point for any such withdrawals.

The study sponsor assures that the key designs of this protocol will be registered on public databases where required by current regulations, and, as applicable, results will be posted.

# 17 APPENDIX B – Sub-Study A

# 17.1 Analysis of Primary Effectiveness Endpoint(s)

The primary objective of this study is to demonstrate noninferiority of monocular photopic BCDVA of the Clareon PanOptix Pro PXYWT0 model compared to Clareon PanOptix at 2 months postoperative (Visit 3A). The primary endpoint is mean monocular photopic BCDVA (logMAR) at 4 m at 2 months postoperative (Visit 3A).

# 17.1.1 Statistical Hypotheses

The null and alternative hypotheses to be evaluated in support of the primary non-inferiority objective are as stated below:

$$H_0: \mu_D \geq \Delta$$

$$H_a$$
:  $\mu_D < \Delta$ 

where,  $\Delta$  refers to the non-inferiority margin, set at 0.1 logMAR, and  $\mu_D$  refers to the mean of the difference between paired observations of each subject's eyes (test minus comparator) for monocular photopic BCDVA at 2 months post implantation.

# 17.1.2 Analysis Methods

The primary effectiveness endpoint, associated with the above hypotheses, will be tested by generating a one-sided 95.1% upper confidence limit based on the mean paired difference (Clareon PanOptix Pro - Clareon PanOptix) using a one-sample t-test. The upper bound of the one-sided 95.1% confidence limit will be compared to the margin, 0.10 logMAR. If the upper bound is less than the margin, the null hypothesis will be rejected and it will be concluded that Clareon PanOptix Pro is noninferior to Clareon PanOptix for monocular photopic BCVDA at 4 m. The difference in means (Clareon PanOptix Pro minus Clareon PanOptix) and the associated one-sided upper confidence limit will be presented.

Document ID: V-CLN-0187723

# 18 APPENDIX C- Sub-Study B

# 18.1 Analysis of Primary Effectiveness Endpoint(s)

The primary objective of this study is to demonstrate noninferiority of monocular photopic BCDVA of the Clareon PanOptix Pro PAYWT0 model compared to Clareon PanOptix at 2 months postoperative (Visit 3A). The primary endpoint is mean monocular photopic BCDVA (logMAR) at 4 m at 2 months postoperative (Visit 3A).

# **18.1.1** Statistical Hypotheses

The null and alternative hypotheses to be evaluated in support of the primary noninferiority objective are as stated below:

$$H_0: \mu_D \geq \Delta$$

$$H_a$$
:  $\mu_D < \Delta$ 

where,  $\Delta$  refers to the noninferiority margin, set at 0.1 logMAR, and  $\mu_D$  refers to the mean of the difference between paired observations of each subject's eyes (test minus comparator) for monocular photopic BCDVA at 2 months post implantation.

# **18.1.2** Analysis Methods

The primary effectiveness endpoint, associated with the above hypotheses, will be tested by generating a one-sided 95.1% upper confidence limit based on the mean paired difference (Clareon PanOptix Pro - Clareon PanOptix) using a one-sample t-test. The upper bound of the one-sided 95.1% confidence limit will be compared to the margin, 0.10 logMAR. If the upper bound is less than the margin, the null hypothesis will be rejected and it will be concluded that Clareon PanOptix Pro is noninferior to Clareon PanOptix for monocular photopic BCVDA at 4 m. The difference in means (Clareon PanOptix Pro - Clareon PanOptix) and the associated one-sided upper confidence limit will be presented.

Contralateral Study of Clareon PanOptix Pro vs. Clareon PanOptix

STUDY ID

ILQ137-C002 Study A

STATISTICAL ANALYSIS PLAN v2 04-Oct-2024

NCT06400745

Statistical Analysis Plan for ILQ137-C002 Title: Contralateral Study of Clareon PanOptix Pro vs. Clareon PanOptix

Executive Summary:

Key Objectives:

The primary objective of the studies under this protocol (Sub-Study A and Sub-Study B) is to demonstrate noninferiority of monocular photopic Best Corrected Distance Visual Acuity (BCDVA) of the 2 Clareon PanOptix Pro models (PXYWT0 and PAYWT0) compared to Clareon PanOptix at 2 months postoperative.

Decision Criteria for Study Success:

Each sub-study will be considered successful if the data indicate a noninferior visual acuity (VA) for the Clareon PanOptix Pro model compared to Clareon PanOptix. Study success will be concluded if the upper bound of the one-sided 95.1% confidence interval does not exceed the noninferiority margin of 0.1 logMAR for mean difference in monocular photopic BCDVA at 2 months postoperative for Clareon PanOptix Pro Intraocular Lenses (IOLs) vs the Clareon PanOptix IOLs. The primary analysis will be based on the All-Implanted Analysis Set (AAS).

Table of Contents

Sta	atistical A	nalysis Pl	an for ILQ137-C002	1							
Ta	ble of Cor	ntents		3							
Li	st of Table	s		5							
1			TVES AND DESIGN								
	1.1		Objectives								
	1.2		Description								
	1.3	-	nization								
	1.4	Masking									
	1.5		Analysis								
2	ANALY		S								
	2.1		reness Analysis Sets								
	2.2		Analysis Set								
3	SUBJEC	_	ACTERISTICS AND STUDY CONDUCT SUMMARIES .								
	3.1	Subject	Disposition and Study Conduct	13							
	3.2		raphics								
	3.3		History and Concomitant Medications								
	3.4		e Eye Biometry								
	3.5		e Visual Acuity and MRSE								
	3.6	Surgical	I Summary	15							
4	EFFECT	TIVENES	S ANALYSIS STRATEGY	16							
	4.1	Effectiv	reness Endpoints – Sub-Study A	16							
		4.1.1	Effectiveness Hypotheses	17							
		4.1.2	Statistical Methods for Effectiveness Analyses								
		4.1.3	Multiplicity Strategy								
	4.2		reness Endpoints – Sub-Study B								
		4.2.1 4.2.2	Effectiveness Hypotheses								
		7.2.2	Statistical Michigas for Effectiveness Alialyses								

	4.5	Interim A	Analysis for Effectiveness	
5 S	AFETY	ANALY	SIS STRATEGY – Sub-Study A and Sub-Study B34	
	5.1	Safety E	ndpoints35	
	5.2	Safety H	Typotheses	
	5.3	Statistica	al Methods for Safety Analyses	
		5.3.1	Adverse Events	

1 STUDY OBJECTIVES AND DESIGN

All study conduct, effectiveness, and safety data will be reported for each sub-study (A and B) separately.

1.1 Study Objectives

Primary Objective: Sub-Study A and Sub-Study B

To demonstrate noninferiority of monocular photopic BCDVA of the Clareon PanOptix Promodels (PXYWT0 and PAYWT0) compared to Clareon PanOptix at 2 months postoperative (Visit 3A).

Secondary Objective:

Not applicable.

Safety Objectives: Sub-Study A and Sub-Study B

To describe the incidence of ocular adverse events including secondary surgical interventions.

1.2 Study Description

This is a prospective, multicenter, randomized, assessor and subject masked, contralateral, active controlled study.

The study protocol contains two sub-studies: sub-study A and sub-study B

- Sub-study A (n = ~66 implanted subjects) Subjects implanted contralaterally with Clareon PanOptix Pro, Model PXYWT0 in one eye and Clareon PanOptix, Model CNWTT0 in the fellow eye
- Sub-study B (n = ~66 implanted subjects) Subjects implanted contralaterally with Clareon PanOptix Pro, Model PAYWT0 in one eye and Clareon PanOptix, Model CNWTT0 in the fellow eye
- Subjects will be randomized in a 1:1 manner to either sub-study A and sub-study B and further randomized to receive Clareon PanOptix Pro or Clareon PanOptix in the first surgical eye, and the second eye will receive the other lens. Subjects will be block randomized by investigation site.

[figure not shown]
The protocol will be executed simultaneously and identically for both sub-studies by the sites. (All testing and assessments will be the same for both sub-studies.) Segregation by sub-study A and sub-study B will only be used for analysis and reporting.

Enrollment will commence at approximately 10 investigative sites. All of the study sites will be located in one country, the United States.

The total duration of a subject's participation in the study is approximately 7 months, attending 9 study visits (which includes the Screening Visit). Subjects will be followed for a total of approximately 6 months postoperatively with primary being assessed at the 2-month (Visit 3A) follow-up visit.

The duration of the entire study is approximately one year.

Figure 1-1 Study Design Flowchart

The schedule of visits is included as Table 10-1 in the appendix.

The purpose of this study design is to establish the safety and effectiveness of two Clareon PanOptix Pro models (PXYWT0 and PAYWT0).

Refer to the study protocol for further details on the rationale for study design.

1.3 Randomization

Only after signing the informed consent form (ICF), a subject will be assigned a subject number by the electronic data capture system (EDC). Lens model will be assigned by randomization via the EDC system on the day of or after the Screening visit if the subject meets all entry criteria.

Subjects will be randomized to one of two sub-studies and to contralateral lens model in a 1:1 ratio. Subjects will be block randomized by investigational site. Subjects at each site will be randomized to one of two sub-studies in a 1:1 ratio. Sub-study A will evaluate Model PXYWT0, and sub-study B will evaluate Model PAYWT0. Subjects randomized to sub-study A will be further randomized to receive Model PXYWT0 or Model CNWTT0 in the first surgical eye, and the second eye will receive the other lens. Similarly, subjects randomized to sub-study B will be further randomized to receive Model PAYWT0 or Model CNWTT0 in the first surgical eye and the second eye will receive the other lens. The 1st surgical eye will be the eye with the worse BCDVA at screening. When the BCDVA is equal between the two eyes, the right eye (OD) will be the 1st surgical eye.

1.4 Masking

This study is assessor-masked and subject-masked.

. Alcon personnel (including biostatistics, masked data manager, and clinical project lead) will also be masked. All other members associated with the study (at the site and the study sponsor) are unmasked.

At the 1st interim lock, unmasking of Alcon personnel will be limited to the subset of subjects who complete the 2-Month postoperative visit for inclusion in the 1st interim analysis. For those subjects not included in the 1st interim analysis, Alcon personnel will remain masked to IOLs implanted in the eye until the 2nd interim study database lock. Masked assessors will be masked to the IOLs implanted until the final database lock.

Subjects will be provided with implant cards by unmasked personnel upon exiting the study and will become unmasked at that time.

Masked study personnel must avoid seeking information that may compromise masking. Unmasked study personnel must not disseminate information that is potentially unmasking to any masked personnel. The masked and unmasked site personnel must coordinate all study activities as necessary to protect masking and minimize bias during the study.

1.5 Interim Analysis

Two interim analyses are planned for this study.

The first interim analysis will be conducted when approximately 40 subjects (approximately 20 in each sub-study, minimum 30 subjects total) complete the 2-Month postoperative visit. This interim analysis is designed to review preliminary safety and effectiveness results for strategic business decision making purposes. There is no intention of stopping the study early. A second interim analysis will be conducted when all subjects complete the 2-Month postoperative visit, at this point treatment arms will be unmasked, and all inferential analysis will be conducted. To control the overall type I error rate (at one-sided alpha = 0.05) the Lan-DeMets method with an O'Brien-Fleming alpha spending function will be utilized to distribute the type I error rate between the first and second interim analyses. The first interim analysis will be conducted when approximately 1/3 of the information fraction (in this case 1/3 of the target sample size) is available, therefore for administrative purposes a one-sided alpha of approximately 0.001 will be spent at the first interim analysis and accordingly the

significance level at the second interim analysis (which is the primary inferential analysis point) will be one-sided 0.049 for all effectiveness endpoints. The power estimates provided below are based on a one-sided 0.049 significance level.

A final analysis will be performed once the 6-Month follow-up is complete, at which time the study database will be considered final and locked to report longer term effectiveness and safety results.

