# 12.4 Effectiveness Analyses

In general, descriptive statistics will be generated using mean, standard deviation, median, minimum, and maximum, for continuous variables. The number in each category and percentage will be reported for categorical variables. Summaries of logMAR VA may include two-sided 95% confidence intervals for the mean difference between treatment groups.

For statistical inference testing, the overall Type I error will be maintained, within each substudy, at the alpha 0.05 level (one-sided) using a sequential testing approach that will be detailed in the statistical analysis plan.

See Appendix B for specific effectiveness analyses related to sub-study A and see Appendix C for specific effectiveness analyses related to sub-study B.

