# 12.7 Interim Analyses and Reporting

The first interim analysis will be conducted when approximately 40 subjects (approximately 20 in each sub-study, minimum 30 subjects total) complete the 2-Month postoperative visit. This interim analysis is designed to review preliminary safety and effectiveness results for strategic business decision making purposes. There is no intention of stopping the study early. A second interim analysis will be conducted when all subjects complete the 2-Month postoperative visit, at this point treatment arms will be unmasked and all inferential analysis will be conducted. To control the overall type I error rate (at alpha = 0.05) the Lan-DeMets method with an O'Brien-Fleming alpha spending function will be utilized to distribute the type I error rate between the first and second interim analyses. The first interim analysis will be conducted when approximately 1/3 of the information fraction (in this case 1/3 of the target sample size) is available, therefore the alpha spend will be approximately 0.001 at the first interim analysis and accordingly the significance level at the second interim analysis (which is the primary inferential analysis point) will be 0.049 for all effectiveness endpoints. The power estimates provided below are based on a 0.049 significance level.

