4.1.2 Statistical Methods for Effectiveness Analyses

Table 4-1 summarizes the primary Supportive analyses using the BAS will be conducted only if the number of eyes excluded from the BAS exceeds 10% of the AAS.

Table 4-1 Sub-Study A – Summary of Analysis Strategy for Primary

Endpoint	Main vs. Supportive	Comparison/	Analysis	Missing
1	Approacha	Statistical	Set	Data
		Method		Approach
Primary				
Mean monocular photopic BCDVA (logMAR) at 4 m	M	One-sample t-test for noninferiority	AAS	Observed data only
at 2 months postoperative (Visit 3A)	S		BAS	

Primary Effectiveness Analyses

The primary effectiveness endpoint, associated with the above hypotheses, will be tested by generating a one-sided 95.1% upper confidence limit based on the mean paired difference (Clareon PanOptix Pro – Clareon PanOptix) using a one-sample t-test. The upper bound of the one-sided 95.1% confidence limit will be compared to the margin, 0.10 logMAR. If the upper bound is less than the margin, the null hypothesis will be rejected, and it will be concluded that Clareon PanOptix Pro is non-inferior to Clareon PanOptix for monocular photopic BCVDA at 4 m. The difference in means (Clareon PanOptix Pro minus Clareon PanOptix), standard error, and the associated one-sided 95.1% upper confidence limit will be presented.

4.2.1 **Effectiveness Hypotheses**

Primary Effectiveness

The null and alternative hypotheses to be evaluated in support of the primary noninferiority objective are as stated below:

$$H_0: \mu_D \ge \Delta$$

 $H_a: \mu_D < \Delta$

where, Δ refers to the noninferiority margin, set at 0.1 logMAR, and μ_D refers to the mean of the difference between paired observations of each subject's eyes (test minus comparator) for monocular photopic BCDVA at 2 months post implantation.

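### Must the second-look level of one-sided 0.049 be changed because Lan-DeMets O'Brien-Fleming spending at 1/3 information gives about 0.0498?

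*SAP*

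**What the plan says.** SAP 1.5 sets the overall error at one-sided 0.05 and says that "the Lan-DeMets method with an O'Brien-Fleming alpha spending function will be utilized to distribute the type I error rate" between the two interim analyses. The first look comes at about 40 subjects, about 20 per sub-study, described as one third of the target. There, "for administrative purposes a one-sided alpha of approximately 0.001 will be spent at the first interim analysis". The SAP then draws the consequence that the "significance level at the second interim analysis (which is the primary inferential analysis point) will be one-sided 0.049 for all effectiveness endpoints".

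Protocol 12.7 follows the same chain and ends with "the significance level at the second interim analysis (which is the primary inferential analysis point) will be 0.049 for all effectiveness endpoints". It does not itself say one-sided; Protocol 12.4 does, requiring the overall error to be "maintained, within each substudy, at the alpha 0.05 level (one-sided").

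The level reaches the primary test as a confidence limit. The SAP Executive Summary states: "Study success will be concluded if the upper bound of the one-sided 95.1% confidence interval does not exceed the noninferiority margin of 0.1 logMAR". Protocol 17.1.2 states: "The upper bound of the one-sided 95.1% confidence limit will be compared to the margin, 0.10 logMAR", and 18.1.2 repeats this for sub-study B. SAP 4.1.2 and 4.2.2 use the same limit and add that "the associated one-sided 95.1% upper confidence limit will be presented".

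Both documents say that early stopping is not intended and place all inferential analysis at the second look. Protocol 7.2.1 adds that the interim analyses will not alter design or conduct.

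**The concern.** The plan names a method and then gives a number that the method does not produce. Someone who programs the named spending function at the stated fraction gets about 0.0498, not 0.049. No information fraction yields both 0.001 at the first look and 0.049 at the second.

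This matters on its face because 0.049 sets the success criterion for both sub-studies and is said to apply to all effectiveness endpoints. A threshold that does not follow from its stated source invites two questions: is type I error still controlled, and which governs, the method or the number?

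**Working it through.** **Inputs**
- Overall alpha 0.05, one-sided (SAP 1.5; Protocol 12.4).
- First look at fraction t of about 1/3, about 20 per sub-study, at least 30 in total (SAP 1.5; Protocol 12.7).
- About 60 evaluable per sub-study, SD 0.08, expected difference 0, margin 0.1 logMAR (Protocol 12.8).

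**1. The plan's own figures.** Subtraction reproduces the pair exactly: 0.05 - 0.001 = 0.049, and 1 - 0.049 = 95.1%. That the sponsor obtained it this way is an inference.

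**2. The named method.** The spend is a(t) = 2[1 - Φ(1.960/√t)]. The second-look critical value c solves P(Z1 < c1, Z2 ≥ c) = 0.05 - a(t), with correlation √t between the looks and c1 the first-look boundary.

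| First look | t | Spend | Second-look level |
|---|---|---|---|
| 20 of 60 | 0.333 | 0.00069 | 0.0498 (z = 1.647) |
| 20 of 66 | 0.303 | 0.00037 | 0.0499 |
| 15 of 60 | 0.25 | 0.00009 | 0.0500 |
| exactly 0.001 spent at 1/3 | 0.333 | 0.00100 | 0.0496 |

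The stated first-look figure is a fair rounding of 0.00069. The second-look figure is not explained by rounding: spends that round to 0.001 (0.0005 to 0.0015, t = 0.317 to 0.381) give levels of 0.0498 to 0.0495. A level of 0.049 needs t = 0.44, where the spend is 0.0031.

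Other readings do not recover the pair at t = 1/3 either. Two-sided 0.05 gives 0.0002 and 0.0499. The classical O'Brien-Fleming boundary gives 0.0021 and 0.0491. Pocock-type spending gives 0.0226 and 0.0340.

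**3. Type I error with the plan's numbers.**
- Nothing tested at the first look: 0.0490.
- 0.001 tested first, then 0.049: 0.0495 at t = 0.25, 0.0494 at t = 1/3, 0.0492 at t = 0.5.
- At any t, the sum of the two levels bounds the error: 0.001 + 0.049 = 0.05.

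Control therefore does not depend on when the first look falls, provided no more than 0.001 is used there.

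**4. Effect on the primary test.** The half-width is t(59) × SD/√n, with SD/√n = 0.08/√60 = 0.010328.
- At 0.049: 1.68126 × 0.010328 = 0.017364.
- At 0.0498: 1.67341 × 0.010328 = 0.017283.
- Difference: 0.00008 logMAR.

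The largest mean difference that still passes is 0.1 - 0.017364 = 0.08264 under the plan, against 0.1 - 0.017283 = 0.08272 under the computed level. Only a result inside that gap would change the conclusion, and the expected difference is 0.

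Protocol 12.8 does not say whether 0.08 is the SD of the paired difference. If it is a per-eye SD and the eyes are uncorrelated (an assumption), the SD of the difference is 0.08 × √2 = 0.113 and the limit moves by 0.00011.

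**5. Power.** With n = 60, power exceeds 99.9% at both levels and under both readings of the SD, which agrees with Protocol 12.8.

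**The case for a change.** The strongest case for a change is that a prespecified plan should not attribute a number to a method that does not give it. The SAP does say that its first-look spend is for administrative purposes, but that phrase qualifies only the 0.001, and Protocol 12.7 lacks it. Nor is 0.049 simply the alpha left to spend. At t = 1/3 that remainder is 0.05 - 0.00069 = 0.0493, and in any case the plan uses 0.049 as a nominal test level, which under Lan-DeMets differs from the increment because the looks are correlated. Describing the pair as a fixed conservative split would take one sentence.

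The description of the derivation is indeed inexact in both documents, and that much stands. The practical risk does not. The analyst is not left to derive a limit: 0.049 is written out in SAP 1.5 and Protocol 12.7, 95.1% is written out in the SAP Executive Summary, SAP 4.1.2 and 4.2.2 and Protocol 17.1.2 and 18.1.2, and the power statements are tied to 0.049. There is one number to program. Calling alpha spent at a look where no test is planned is loose, but the error stays below 0.05 even if 0.001 is tested there.

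**Conclusion.** No change to the plan. The arithmetic point is right: 0.049 is not the output of Lan-DeMets O'Brien-Fleming spending at one third of the information, which gives about 0.0498. The slip lies in how the number is explained, and the number itself is consistent, prespecified and slightly conservative. Overall error is at most about 0.0495, the upper limit moves by about 0.0001 logMAR against a margin of 0.1, and power remains above 99.9%.

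Neither possible edit earns its place. Rewording the derivation alters no result. Moving to 0.0498 would relax the success criterion for both sub-studies through a protocol amendment, with no material gain. The documents do not say whether the first interim has taken place, so the change might also follow an unmasked look.

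This rests on 0.049 being applied as written, on no more than 0.001 being used at the first look, and on about 60 evaluable subjects with an SD of the paired difference between 0.08 and 0.113.
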